## **3.2 Primary Outcome Measure**

The primary outcome measure is the occurrence of cardiopulmonary events. It will be measured as the occurrence of any cardiopulmonary event, within 72 hours of presentation to the ED, including:

Cardiac arrest

Sustained ventricular tachycardia (VT)

Hypotension requiring inotropes or intraaortic balloon pump (IABP) insertion

Intubation or mechanical ventilation

Complete heart block

Bradycardia requiring insertion of a pacing wire or external pacing, and

Percutaneous coronary intervention (PCI) or coronary artery bypass surgery (CABG).

For the primary outcome measure of occurrence of cardiopulmonary events, binary logistic regression will be used to estimate the probability that a cardiopulmonary

event has occurred given the values of explanatory variables, given by the following equation:

- $Y$  is the primary outcome measure  
 $Y_i = 1$  if a cardiopulmonary event has occurred  
 $Y_i = 0$  if there is no cardiopulmonary event
- $\pi_i$  = the probability of a cardiopulmonary event
- $X = (X_1, X_2, \dots, X_k)$  being the set of explanatory variables

*Model:*

$$\text{logit}(\pi_i) = \beta_0 + \beta_1 x_{i1} + \dots + \beta_k x_{ik}$$

A Receiver Operating Characteristic Curve will be constructed and the area under the curve will be calculated to assess the model sensitivity.

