### **3.7 Sample Size**

Approximately 760 subjects are planned to be enrolled in the study to provide 634 subjects in the final analysis.

When the sample size is 634, the logistic regression test of  $\beta=0$  ( $\alpha = 0.050$  two-sided) will have 80% power to detect a  $\beta$  of 0.747 (an odds ratio of 2.111); this assumes that one normally distributed covariate  $x$  is being added to the model after adjustment for prior covariates, that its multiple correlation with covariates already in the model is 0.500 and, that the proportion of successes at the mean of  $x$  is 0.050.

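### Section 3.2 takes the AUC of a fitted model, apparently in the same subjects, with no optimism correction and no limit on the number of predictors; the upward bias ranges from negligible to large depending on that number

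*Combined protocol and SAP*

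**What the plan says.** - **Section 3.2** defines a binary logistic regression of any cardiopulmonary event within 72 hours on explanatory variables X1 to Xk. The variables are not named and k is not given. The section then adds: "A Receiver Operating Characteristic Curve will be constructed and the area under the curve will be calculated to assess the model sensitivity". It does not mention the existing algorithm's score.
- **Section 3.7** gives the size: "Approximately 760 subjects are planned to be enrolled in the study to provide 634 subjects in the final analysis". The power statement concerns one covariate that "is being added to the model after adjustment for prior covariates", and whose "multiple correlation with covariates already in the model is 0.500". The assumed event proportion at the mean of that covariate is 0.050.
- **Sections 2.1.4.1 and 3.1** give the primary objective as verifying an algorithm that already exists. Section 1.1 explains that it was developed and tested only in Singaporean patients.
- **Sections 2.3 and 2.3.2.1** list the data to be recorded. They do not say which items are explanatory variables.

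Neither protocol nor analysis plan mentions a second data set, a holdout sample, cross-validation, a bootstrap, an optimism correction, a confidence interval for the AUC, or a limit on k.

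**The concern.** Maximum likelihood chooses the coefficients that best separate events from non-events in the sample at hand, including separation due to chance. An AUC calculated in those same subjects counts the chance part as discrimination. The effect grows with the number of predictors and shrinks with the number of events, and this study expects few events.

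The study exists to show whether an algorithm carries over to a new population. An AUC that contains fitting bias could look acceptable even if the algorithm transfers poorly, and it would not be reproduced in the next cohort. Refitting also changes the question: the AUC of a model with locally estimated coefficients describes that new model, not the existing algorithm.

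**Working it through.** **1. The plan's own sample size.** Inputs from section 3.7: two-sided alpha 0.05, power 80%, b = 0.747 (exp(0.747) = 2.111), p = 0.050, correlation term 0.500. Whittemore/Hsieh (1989) formula for one normal covariate:

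- d = (1 + (1 + b²)·exp(5b²/4)) / (1 + exp(−b²/4)) = 2.209
- n = (1.960 + 0.842·exp(−b²/4))² · (1 + 2pd) / (p·b²) = 7.247 × 1.221 / 0.0279 = 317.1
- 317.1 / (1 − 0.50) = 634.2, which matches 634.

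The match needs 0.500 to be the *squared* multiple correlation. Read literally as R = 0.5, n = 317.1/0.75 = 423. That wording needs clarifying, but it does not affect what follows.

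**2. Expected events.** The documents state no count.

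- At the planning rate: 634 × 0.050 = 31.7.
- Averaging the rate over a normal covariate with b = 0.747 gives 6.25%: 634 × 0.0625 = 39.6.
- From the earlier chest-pain study in section 1.1 (sensitivity 0.880, specificity 0.680, PPV 0.195), prevalence = 0.195 × 0.320 / (0.880 × 0.805 + 0.195 × 0.320) = 0.081, or 51 events. Its NPV of 0.985 gives 0.079, or 50 events.

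**3. How large k could be.** Section 3.7 implies at least 2. The admission items in section 2.3 give 3 demographic + 1 smoking + 7 drug classes + 12 history items + 5 others (GCS, chest pain, symptom onset, pain score, MEWS) = 28. This is an upper bound drawn from a data-collection list, not a planned model.

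**4. Bias with one real predictor.** Simulation: n = 634, one predictor at OR 2.111 per SD, event rate 0.05 at its mean, k − 1 independent normal noise predictors, maximum-likelihood fit. AUC was taken in the fitting sample and in 20,000 new subjects (600 runs per row; the k=28 row is from a separate run).

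| k | Same subjects | New subjects | Difference |
|---|---|---|---|
| 1 | 0.700 | 0.708 | −0.008 |
| 2 | 0.700 | 0.694 | 0.006 |
| 5 | 0.718 | 0.678 | 0.040 |
| 10 | 0.738 | 0.662 | 0.076 |
| 20 | 0.773 | 0.635 | 0.138 |
| 28 | 0.796 | 0.630 | 0.166 |
| 30 | 0.805 | 0.619 | 0.186 |

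Repeat runs gave 0.715 against 0.679 at k=5 (0.036) and 0.739 against 0.664 at k=10 (0.075). At k=2 a repeat put the bias at about 0.015, so differences of about 0.01 are within simulation error. At an 8% event rate, k=10 gave 0.729 against 0.667 (0.062). With binary predictors, k=10 gave 0.751 against 0.652 (0.099).

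**5. Noise predictors only (true AUC 0.50).** Mean same-sample AUC, 1,000 runs per cell:

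| k | 32 events | 40 events | 51 events |
|---|---|---|---|
| 2 | 0.564 | 0.557 | 0.553 |
| 5 | 0.609 | 0.598 | 0.586 |
| 10 | 0.655 | 0.641 | 0.627 |
| 20 | 0.720 | 0.700 | 0.679 |
| 30 | 0.765 | 0.742 | 0.718 |

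If an ordinary 95% interval (Hanley-McNeil) were attached, its lower limit would exceed 0.5 in about half of the noise-only studies at k=5 and about 91% at k=10, for 32 or 40 events. The intended share is about 2.5%.

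**6. The fixed score for comparison.** A worthless score evaluated without refitting gave a mean AUC of 0.50 (5th to 95th percentile 0.42 to 0.58) at 32 and at 40 events. None of 4,000 runs at either count reached 0.70, and the lower limit exceeded 0.5 in about 2%.

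**The case against.** The strongest reply is that the size of the bias depends on a number the plan does not give. The stated purpose is to verify an existing algorithm, and section 1.1 says the study will look at that algorithm's sensitivity and specificity. If its score is the only predictor and carries real signal, the logistic fit merely rescales it, the ranking of subjects is unchanged, and the AUC is essentially unbiased. That is correct, and the text does not rule it out.

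Other parts of the reply also stand:

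- Section 3.7 states a power assumption. It points to more than one predictor but does not define the model behind the ROC curve or say how many predictors it holds.
- The 28 items are data to be recorded. No section proposes entering them all.
- The 32 to 40 events follow from a planning rate; about 51 is also plausible, though that figure comes from chest-pain patients only.
- The AUC is not declared to be the primary result. The Protocol Summary names regression as the primary analysis, section 3.7 powers the test of a coefficient, and no AUC target is set.
- Evaluation in the same subjects is the plain reading because no other data are described, but it is not stated outright.

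A reader might therefore infer that the reported AUC will certainly be inflated, or that it will look good even if every predictor is noise. The documents do not support either as a fact. The first is conditional on k. The second needs about 20 noise predictors before the mean reaches 0.70 at 32 to 40 events, and no section proposes such a model.

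What does not stand is that this is only missing detail. The procedure as written gives an upward-biased AUC for any model with several predictors, and nothing in the plan prevents or corrects that.

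**Conclusion.** The point holds conditionally. With 634 subjects and about 40 events, the expected upward bias is negligible for the score alone, about 0.04 at k=5, about 0.08 at k=10, and about 0.17 in the worst case of all 28 or so listed variables. Pure-noise predictors give a mean AUC of about 0.66 at k=10 with 32 events (0.63 with 51).

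These figures assume that the AUC is taken in the fitting sample, that one predictor has the planned odds ratio, and that the rest are independent normal noise with no variable selection. More events reduce the bias without removing it. In a noise-only check with mostly binary predictors, with and without correlation, the mean AUC at a 5% event rate was 0.66 at k=10 and 0.76 at k=28, essentially the same as with normal predictors.

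The underlying gap is that the predictor set is not named. The plan should close it, and add the correction, before outcome data are analysed.

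**What to change.** 1. In section 3.2, make the main performance result the AUC of the existing algorithm's score, used as it stands without refitting, with a 95% confidence interval. At a true AUC of 0.70 the expected half-width is about 0.10 with 32 events and 0.09 with 40.
2. For any fitted model with predictors beyond the score, list the predictors in advance. Keep them few relative to the expected events, or use penalised fitting (Firth or ridge).
3. Report the bootstrap optimism-corrected AUC as that model's result, repeating any variable selection within each resample, and state the number of resamples in the plan. Give the same-sample AUC only as a descriptive figure.

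The cost is a few lines of text, a little computing and a lower reported AUC. No additional patients, data or procedures are needed.

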### 3.3 Secondary Outcome Measure

The secondary outcome measure of the frequency of any cardiac event will be measured as the occurrence of any cardiac and cardiac-related events, not limited to:

1. In-hospital Death
2. In-hospital Cardiac Arrest
3. Composite cardiovascular outcome or intervention (Lethal Arrhythmias , Acute Pulmonary Edema, Cardiogenic Shock, Myocardial Infarction, Percutaneous Coronary Intervention, Coronary artery Bypass Surgery , New or Recurrent MI, Recurrent Ischemia requiring Revascularization)

For the secondary outcome measure of frequency of any cardiopulmonary event, multiple linear regression will be used to estimate the probability that an increase in the number of cardiopulmonary events given the values of explanatory variables, given by the following equation:

- $Y_i$  is the number of cardiopulmonary events
- $\pi_i$  = the probability of a cardiopulmonary event
- $X = (X_1, X_2, \dots, X_i)$  be the set of explanatory variables
- $p$ =number of  $\beta$  coefficients in the model (including the intercept)

*Model:*

$$y_i = \beta_0 + \beta_1 x_{i1} + \beta_2 x_{i2} + \dots + \beta_{p-1} x_{ip} + \epsilon_i$$

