### **2.1.6 Secondary Outcomes**

#### **2.1.6.1 Frequency of Cardiopulmonary Events**

The number of cardiac events will be measured as the occurrence of any cardiac and cardiac-related events, not limited to:

1. In-hospital Death

2. In-hospital Cardiac Arrest

3. Composite cardiovascular outcome or intervention (Lethal Arrhythmias , Acute Pulmonary Edema, Cardiogenic Shock, Myocardial Infarction, Percutaneous Coronary Intervention, Coronary artery Bypass Surgery , New or Recurrent MI, Recurrent Ischemia requiring Revascularization)

\*all within 72 hours of presentation to the ED

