#### **2.1.6.2 Cardiac Arrest**

Cardiac arrest will be defined as the event of developing ventricular fibrillation, having a sudden unexpected death, or having a resuscitation event requiring cardiopulmonary assistance (chest compressions and/or defibrillation).

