## 2.3 Study Procedures

Schedule of Events			
Hospital Stay Status	Admit	During	Discharge/ Withdrawal
Inclusion/Exclusion Criteria	X		
Informed Consent	X 		
Study Evaluations			
Demographics (date of birth/age, gender and ethnicity)	X		
Smoking status	X		
ED diagnosis (primary)	X		
Final diagnosis (primary)			X
Medications including beta-blockers, combined alpha and beta-blockers, digitalis, calcium channel blocker, bronchodilators, amiodarone, other anti-arrhythmics	X	X	X

Medical history, specifically a history of ischemic heart disease, diabetes, hypertension, dyslipidemia, stroke, cancer, respiratory disease, renal disease, congestive heart disease, PCI, CABG, MI)	X		
Physical exam [REDACTED]	X		
Glasgow Coma Score (GCS)	X		
Blood labs; specifically troponin and/or CKMB if available	X		
12-lead ECG (if patient is reporting chest pain)	X 		
Continuous 3-lead ECG recording of at least five minutes	X		
Chest Pain	X		
Symptom onset/peak within 24 hours of presentation	X		
Pain score	X		
MEWS Score	X		
Cardiopulmonary events (acute pulmonary edema, lethal arrhythmias, cardiogenic shock, myocardial infarction, percutaneous coronary intervention, coronary artery bypass surgery, recurrent ischemia requiring revascularization)	X	X	X
In-hospital cardiac arrest		X	
In-hospital death		X	
Status changes (admitted to ICU, admitted to ward, etc.)		X	
Length of stay			X
Adverse Events	X	X	X

1 Every effort will be made to ensure that consent is received from the patient or patient's legally authorized representative (LAR) within 24 hours of patient enrollment. If the patient or LAR refuses consent the patient will be withdrawn from the study.

[figure not shown]
2 If applicable

3 Serious adverse events must be reported to the Sponsor within 24 hours of becoming aware of the event, but no later than 10 days after the event.

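### Section 3.3 describes a linear regression on an event count as estimating a probability, and gives no closed event list or counting rule, so analysts can derive different counts from the same record

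*Combined protocol and SAP*

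**What the plan says.** Section 3.3 gives the only model for the secondary objective.

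- **Stated purpose of the model:** "multiple linear regression will be used to estimate the probability that an increase in the number of cardiopulmonary events", given the explanatory variables.
- **Response in that model:** Y "is the number of cardiopulmonary events". The equation is an ordinary linear one with an error term. A probability symbol, pi, is defined next to it but is absent from the equation.
- **How the outcome is measured:** it "will be measured as the occurrence of any cardiac and cardiac-related events, not limited to" three numbered items. These are in-hospital death, in-hospital cardiac arrest, and a composite whose components include "Myocardial Infarction, Percutaneous Coronary Intervention, Coronary artery Bypass Surgery , New or Recurrent MI, Recurrent Ischemia requiring Revascularization".

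Section 2.1.6.1 puts both readings in one sentence: "The number of cardiac events will be measured as the occurrence of any cardiac and cardiac-related events, not limited to". It adds the time limit, "all within 72 hours of presentation to the ED", which Section 3.3 does not repeat.

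Section 2.1.6.2 defines cardiac arrest as "the event of developing ventricular fibrillation, having a sudden unexpected death, or having a resuscitation event requiring cardiopulmonary assistance".

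The data collection lists in Sections 2.3 and 2.3.2.1 name "acute pulmonary edema, lethal arrhythmias, cardiogenic shock, myocardial infarction, percutaneous coronary intervention, coronary artery bypass surgery, recurrent ischemia requiring revascularization", with in-hospital arrest and in-hospital death as separate entries. They have one MI label where Section 3.3 has two.

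Section 3.1 makes the secondary objective an assessment of the algorithm. Section 3.3 names no explanatory variable and no standard-error method.

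**The concern.** The section mixes two targets. A probability belongs to a 0/1 outcome, whether any event occurred. A linear model for a number of events estimates a mean count. A reader of the eventual result could not tell from the plan which of the two it was meant to be.

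If the count is intended, it still has to be derived from the record. The list is open and its labels overlap, and no section says whether the composite counts once or by component, or whether repeats count. Two competent analysts could then report different slopes from the same patients, and the rule could be chosen after the data are seen.

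A smaller matter is precision. The default interval from a linear model assumes equal residual spread at every score. If events are rare and related to the score, spread rises with risk and the default interval can be too narrow.

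**Working it through.** **1. What the model estimates.** Section 3.2 uses pi inside a logit, where it has a role. Section 3.3 lists pi again, but its equation has y on the left and a linear predictor plus error on the right. The slope is therefore a difference in mean Y per unit of x. That is a legitimate quantity, but it is a probability difference only if Y is 0/1, and Section 3.3 defines Y as a number.

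**2. What counts as one event.** Applying the plan's own labels to two patients:

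| Reading | VF arrest, new MI, PCI | Sudden death in VF |
|---|---|---|
| Occurrence of any event | 1 | 1 |
| Three numbered items, each once | 2 (arrest, composite) | 2 (death, arrest), or 3 if the VF also enters the composite as a lethal arrhythmia |
| Labels in Sections 2.3 and 2.3.2.1 | 4 (arrest, lethal arrhythmia, MI, PCI) | 3 |
| Labels in Section 3.3 | 5 (the same four plus New or Recurrent MI) | 3 |

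The overlap of arrest, lethal arrhythmia and death arises under every count reading. The overlaps of MI with New or Recurrent MI, and of PCI or CABG with recurrent ischemia requiring revascularization, matter only if the composite is unpacked.

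**3. Default intervals.** The plan states no figure for the secondary analysis. The inputs are n = 634 and beta = 0.747 (Section 3.7, written for the primary logistic model; exp(0.747) = 2.111, as stated there) and sensitivity 0.880 and specificity 0.680 at a score of 4 or more (Section 1.1). As a check on Section 1.1, solving 0.88p/(0.88p + 0.32(1 − p)) = 0.195 gives p = 0.081. The implied negative predictive value is 0.985, as stated. The event rate for the secondary outcome is an assumption, shown over a range.

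*Dichotomised score, 0/1 outcome, 5% rate.*
- Share with a high score: q = 0.88 × 0.05 + 0.32 × 0.95 = 0.348.
- Risks: p1 = 0.044/0.348 = 0.1264 and p0 = 0.006/0.652 = 0.0092.
- Variances p(1 − p): 0.1105 and 0.0091.
- True n × variance of the slope: 0.1105/0.348 + 0.0091/0.652 = 0.331.
- Default n × variance: (0.348 × 0.1105 + 0.652 × 0.0091)/(0.348 × 0.652) = 0.196.
- Standard-error ratio: √(0.331/0.196) = 1.30.
- Approximate coverage: 2Φ(1.96/1.30) − 1 = 87%.

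Simulation at n = 634 agrees, with 86% coverage and an HC3-to-default ratio of 1.31. A count outcome (1 to 5 in affected patients) gives the same result.

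| Setting | Default 95% CI covers | HC3 / default SE |
|---|---|---|
| Dichotomised score, rate 5% | 86% | 1.31 |
| Dichotomised score, rate 20% | 92% | 1.11 |
| Dichotomised score, rate 30% | 94% | 1.02 |
| One continuous score, beta 0.747, 5% at its mean | 90–91% | 1.15 |
| Same plus a covariate correlated 0.5 or 0.707 with it (assumed), 5% | 92–94% | 1.04–1.11 |
| One continuous score, 20% at its mean | 94–96% | 0.99–1.02 |
| Continuous score, no association, 5–30% | 94.6–95.2% | about 1 |

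HC3 intervals covered about 93% to 96% throughout.

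**The case against.** The strongest reply is that the plan is less empty than this suggests. Section 3.3 states Y and writes out the equation. The probability clause and the spare pi look carried over from Section 3.2. Event types are listed, Section 2.1.6.1 supplies the 72 hours and Section 2.1.6.2 defines arrest. A numbered list ending in a composite is most naturally read as three items, with the composite counted once. Much of this stands, and it limits the point in several ways.

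- A reader might infer that the secondary analysis has no target, or that events are undefined. The documents do not support that. What is missing is a closed list and a counting rule.
- A reader might multiply the Section 1.1 risk difference (0.195 − 0.015 = 0.18) by 1 to 5 and say the reported effect could lie anywhere from 0.18 to 0.90 events. That requires every affected patient to have the arrest, MI and PCI course and the composite to be unpacked. It also borrows risks from a chest-pain cohort with another endpoint. It is an extreme illustration, not an expected size.
- A reader might infer that a linear model is invalid for a count, or that false positives are inflated. The slope is a valid difference in means, and coverage is near nominal when there is no association.
- Section 3.3 specifies multiple regression. The 86% figure needs a dichotomised score, no other covariate and a 5% rate; with a correlated covariate the shortfall is small. Robust errors are a cheap safeguard, not a demonstrated necessity.
- Unnamed explanatory variables are equally a feature of Section 3.2 and are a wider issue than this one.

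The objection does not remove the incorrect probability statement, the clash between occurrence and number, the open list, or the overlap of arrest, lethal arrhythmia and death, which remains under the three-item reading.

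**Conclusion.** The point holds as a defect of specification in the secondary analysis. As written, Section 3.3 attributes to a linear count model a quantity that it does not estimate, and no other section supplies a rule for forming the count. The size is best expressed per patient: a ventricular fibrillation arrest with a new MI treated by PCI scores 1, 2, or 4 to 5, depending on the reading.

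The interval question is secondary and conditional. At n = 634 and a 5% rate, default coverage is about 86% (dichotomised score), 90% (one continuous score) or 92–94% (with a correlated covariate). It is about nominal at a 20% rate with a continuous score, or with no association. These figures rest on an assumed event rate, on accuracy figures from a different cohort and endpoint, and on an effect size borrowed from the primary analysis.

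The primary logistic analysis does not depend on any of this. The text should be corrected before analysis, but the point does not threaten the study's main result.

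**What to change.** Amend Section 3.3 as follows. The linear model stays.

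1. Delete the probability wording and pi. State that the model estimates the difference in mean number of listed event types per patient within 72 hours of presentation, per unit of the algorithm score. Enter that score as the explanatory variable of interest (an addition, since none is named now).
2. Make the list closed, and count each of the three numbered items (in-hospital death, in-hospital cardiac arrest, composite) at most once per patient, so that Y runs from 0 to 3. State that an arrest ending in death scores both items, and that a ventricular fibrillation already counted as arrest is not counted again as a lethal arrhythmia. The first example above then scores 2, and so does the second. Align Section 2.1.6.1 with this wording.
3. Report HC3 standard errors and 95% intervals.

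**Cost.** SAP wording, a short derivation and one software option. Intervals would be about 4% to 31% wider at a 5% event rate, and hardly different at 20% with a continuous score. Components within the composite, and repeat events, are not counted separately in the model, but components can be shown in the counts and percentages that Section 3.1 already plans. Y remains a count and not a severity scale, since an early death leaves less time for other events. The 72-hour limit needs event times, which Sections 2.3 and 2.3.2.1 do not list by name, but the primary outcome needs them too.

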#### **2.1.2 *Scope and Duration***

This is a prospective, multi-center, observational study.

Enrollment in this study is expected to take approximately 18 months. Subjects are enrolled upon arrival to the emergency department and followed for 72 hours.

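### Section 3.3 fits constant-variance linear regression to a sparse 72-hour event count, so interval estimates are unreliable (probably too narrow under the plan's own inputs) and fitted counts can be negative

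*Combined protocol and SAP*

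**What the plan says.** Section 3.3 defines the response by stating that Y "is the number of cardiopulmonary events". It then says that "multiple linear regression will be used", with the stated aim of estimating a probability from a set of explanatory variables, and it writes the model as a linear predictor plus an error term. The explanatory variables are not listed.

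The same section says that the outcome "will be measured as the occurrence of any cardiac and cardiac-related events, not limited to" a list of death, cardiac arrest and a composite. The text therefore treats the outcome as both a count and an occurrence. The observation window is short: "Subjects are enrolled upon arrival to the emergency department and followed for 72 hours" (2.1.2).

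Section 3 names no count model, robust variance, transformation or residual check. No event rate, power or sample size is given for the secondary outcome. The only planning rate is for the primary binary outcome in 3.7, where "the proportion of successes at the mean of $x$ is 0.050" and the effect is "an odds ratio of 2.111".

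**The concern.** Ordinary least squares takes its standard errors from a single error variance shared by all subjects. A sparse count does not behave that way: subjects with a higher expected count also have a larger variance. When the score predicts events, the error variance changes along the score, and the model-based standard error no longer measures the sampling spread of the slope. A straight line through counts that are mostly zero can also fall below zero for low-risk subjects.

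This regression is the only inferential analysis given for the secondary objective, which is to assess the algorithm against event frequency. The error bars fail when the algorithm works, which is the case the study hopes to show. Settling what counts as one event, or correcting the reference to a probability, would not cure this while the linear model for a count stays.

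**Working it through.** **1. The plan's own figure.** Section 3.3 has no figure to reproduce, so the inputs come from 3.7. These are P = 0.05, slope b = 0.747 per SD, two-sided 5% level, 80% power and n = 634. The Hsieh formula for one normal covariate is N = (1.960 + e^(−b²/4) × 0.842)² × (1 + 2Pδ) / (P b²), where δ = [1 + (1 + b²) e^(5b²/4)] / [1 + e^(−b²/4)]. With b² = 0.558, δ = 2.209 and N = 317.1. Dividing by 1 − 0.5 gives 634.2, so 634 reproduces when the stated 0.500 is used as a squared multiple correlation. Used as an unsquared correlation, it gives 423. That side point does not affect what follows.

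**2. Share of zeros (inferred, not stated).**
- From 3.7: averaging the logistic risk over normal x, with 5% at the mean and slope 0.747, gives 6.2% with an event. That is about 94% zero, or 634 × 0.0624 ≈ 40 subjects with an event.
- From the chest-pain cohort in 1.1 (sensitivity 0.880, specificity 0.680, PPV 0.195, NPV 0.985): the PPV gives 0.195 × 0.320 / (0.880 × 0.805 + 0.195 × 0.320) = 0.0624 / 0.7708 = 8.1%. The NPV gives 0.680 × 0.015 / (0.985 × 0.120 + 0.680 × 0.015) = 0.0102 / 0.1284 = 7.9%. That is about 92% zero.
- The share scoring positive in that cohort is 0.880 × 0.081 + 0.320 × 0.919 = 36.5%.

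**3. Binary score, by formula.** Let q be the share positive, and let v₁ and v₀ be the variances in positives and negatives. For the difference in means, the true variance divided by the model-based variance is

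[(1 − q)v₁ + q v₀] / [q v₁ + (1 − q)v₀].

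Take Poisson variances equal to the risks in 1.1: v₁ = 0.195 (the PPV) and v₀ = 0.015 (1 − NPV). With r the square root of that ratio, approximate coverage is 2Φ(1.96/r) − 1.

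| Share positive | Variance ratio | True SD / model SE | Coverage, formula | Coverage, simulated |
|---|---|---|---|---|
| 20% (assumed) | 0.159/0.051 = 3.12 | 1.77 | 73% | 68–74% |
| 36.5% (implied by 1.1) | 0.1293/0.0807 = 1.60 | 1.27 | 88% | 86–88% |
| 50% (assumed) | 1.00 | 1.00 | 95% | 94–95% |
| 70% (assumed) | 0.069/0.141 = 0.49 | 0.70 | 99% | 99% |

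Simulation at 36.5% positive gave a ratio of up to 1.28.

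**4. Normal score, by simulation.** With n = 634 and slope 0.747, a subject with any event has either exactly one or 1 + Poisson(0.5) events. That multiplicity is an assumption.

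| Risk at mean of x | Zeros | True SD / model SE | Coverage | Negative fits | HC3 coverage |
|---|---|---|---|---|---|
| 5% (from 3.7) | 94% | 1.15–1.18 | 90–91% | 7% | 94% |
| 10% (assumed) | 88% | 1.08–1.10 | 92–93% | 5% | 94–95% |
| 20% (assumed) | 78% | 0.98–1.00 | 95% | 3% | 95% |

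With strongly overdispersed counts (an assumption), model-based coverage fell to about 86%. Basic sandwich standard errors gave about 91%.

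**5. No association.** With slope zero, the error variance is constant in this setting. The linear-model test rejected in 4.5% to 5.2% of runs. For a null covariate beside a predictive one (correlation 0, 0.5 or 0.71), it rejected in 4.6% to 5.5%.

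**The case against.** The strongest reply has four parts.

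- **Section 3.3 promises no confidence interval or p-value.** The only 95% intervals named in section 3 are for means of continuous variables (3.1). This is true. However, any precision reported from the stated model would use these standard errors unless the plan says otherwise.
- **The direction of the error is not fixed.** A reader might infer that many zeros always make least-squares intervals too narrow. The documents do not support that. Intervals are too narrow when the high-variance subjects also have the most leverage. The tables show nominal coverage at 50% positive or at a 20% event risk, and over-coverage at 70% positive. The score's form and distribution in this study are unknown. This part stands and limits the claim.
- **The zero share is not in the plan.** A reader might take nine in ten zeros as a stated fact. It is inferred from two other outcomes. The secondary list differs from the primary one (it adds death, infarction, pulmonary edema and cardiogenic shock) and is open-ended, so the event rate could be higher. This stands.
- **P-values.** A reader might infer that the model produces false-positive findings. The null runs do not support that, because error stayed close to 5%.

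It can also be said that choosing a count model is premature while 3.3 calls the outcome both a number and an occurrence. That is fair, and the fix covers both readings.

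**Conclusion.** The point holds for interval estimates and predictions, not for tests of no association. A constant-variance linear model does not match a sparse, non-negative count, and the plan names no safeguard.

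Under the inputs the documents supply, intervals would be too narrow. The true spread is about 1.15 to 1.28 times the model standard error, coverage is about 87% to 91% instead of 95%, and about 7% of fitted counts are negative at slope 0.747. These figures assume that the primary planning rate, or the earlier cohort's accuracy, carries over to the secondary count. They also assume few repeat events per subject. Outside those inputs the intervals may be about right or too wide, so unreliable is the safe general word and too narrow is the likely case. Confidence in the mismatch is high; confidence in its direction is moderate. Because the analysis is secondary and cheap to correct, it should be changed, but it does not threaten the primary result.

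**What to change.** In 3.3, state first whether the outcome is a count or an occurrence, then name the model that matches:

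- **Count, as Y is now defined:** replace the linear model with a log-linear count model, either Poisson with robust sandwich standard errors or negative binomial. Keep the same explanatory variables and report rate ratios with 95% confidence intervals. This also removes negative fitted counts.
- **Count, with a mean difference preferred:** keep the linear model and state that HC3 robust standard errors will be used. Coverage was about 94% under the planning inputs. Negative fits remain possible.
- **Occurrence:** use logistic regression as in 3.2.

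The cost is a sentence or two of SAP text and routine SAS procedures, with no new data or subjects. For the retained linear model, intervals may be about 15% to 30% wider under the planning inputs, which is the width needed for roughly their stated coverage.
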